## 4 GENERAL STATISTICAL CONSIDERATIONS

Summary outputs, where possible, will be presented by neonate groups (term and pre-term) and overall. No formal hypothesis testing will be performed. Continuous data will be described using descriptive statistics (n, mean, standard deviation [SD], median, minimum, and maximum). Categorical data will be described using the patient count and percentage in each category. Non-zero percentages will be rounded to one decimal place, except 100%, which will be displayed without any decimal places. For the summary statistics of all numerical variables unless otherwise specified, minimum and maximum will be displayed to the same level of precision as reported, up to a maximum of three decimal places. Mean and median will be displayed to one level of precision greater than the data collected, up to a maximum of three decimal places. Standard deviation will be displayed to two levels of precision greater than the data collected, up to a maximum of three decimal places.

When count data are presented, the percentage will be suppressed when the count is zero, to draw attention to the non-zero counts. A row denoted 'Missing' will be included in count tabulations where specified in the table shells, to account for dropouts and missing values. The denominator for all percentages will be the number of patients in the population of interest, unless otherwise specified.

All data will be displayed in listings sorted by neonate groups (term and pre-term) and subject ID.

## 4.1 Sample size justification

This study is not powered for inferential statistical analysis. The sample size (eight patients; two term and six pre-term) is considered adequate to evaluate the safety of ceftobiprole in neonates and infants aged  $\leq 3$  months with LOS.

## 4.2 Analysis populations

### 4.2.1 Intent-to-treat population / Safety population

The Intent-to-treat (ITT) / Safety population consists of all enrolled patients who received at least one dose of ceftobiprole.

### 4.2.2 Clinically Evaluable population

The Clinically Evaluable (CE) population consists of patients in the ITT population who received at least 48 hours of study drug and had a completed overall clinical outcome assessment at the TOC visit, no major protocol deviations, and no concomitant systemic non-study antibiotic therapy.

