## 5.6 Efficacy assessments

### 5.6.1 Overall clinical outcome

At the EOT and TOC visits, the Investigator must assess the overall clinical outcome as:

- ***Clinical cure***
  - Signs and symptoms of LOS improved or normalised to an extent that no further antibacterial therapy is required
- ***Clinical failure***
  - Discontinuation of study treatment and requirement for non-study antibacterial therapy because of:
    - Insufficient therapeutic effect associated with study treatment, including persistence or worsening of signs and symptoms of LOS
    - AE related to the study treatment
  - Death attributable to LOS

- ***Unevaluable***

- Study data not available for evaluation of efficacy for any reason, including:
  - Lost to follow-up
  - Received < 48 hours of study treatment
  - Concomitant treatment with a systemic antibacterial administered for a reason other than LOS, which is active against the isolated LOS pathogen, or in the absence of microbiological evaluation, is active against common LOS pathogens
  - Diagnosis of any of the following conditions after enrollment in the study and discontinuation of study treatment: ventilator-associated pneumonia, meningitis, brain abscess, osteomyelitis, infective endocarditis, or necrotising enterocolitis
  - Death in which LOS is clearly non-contributory
  - Absence of clinical assessment for any reason

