#### 8.2.2 Clinically Evaluable (CE) population

Patients in the ITT population who received at least 48 hours of study treatment (i.e., four or six infusions of ceftobiprole as applicable) and had a completed overall clinical outcome assessment at the TOC visit, no major protocol deviations, and no concomitant systemic non-study antibiotic therapy.

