### 3.2.2 Secondary endpoints

The pharmacokinetics secondary endpoints are:

- Plasma levels of ceftobiprole, ceftobiprole medocaril, and open-ring metabolite (PK population).

The efficacy secondary endpoints are:

- Clinical cure rate at the EOT and TOC visits [Intent-to-treat (ITT) and Clinically Evaluable (CE) populations]
- ACM through Day 28 (ITT population)
- Microbiological eradication or presumed eradication rate at the EOT and TOC visits (Microbiological Intent-to-treat (mITT) and Microbiologically Evaluable (ME) populations)
- Improved signs and symptoms of LOS at the Day 3, EOT, and TOC visits (ITT and CE populations).

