### 4.2.4 Microbiologically Evaluable population

The ME population consists of all patients in the CE population with a causative pathogen identified at baseline and a microbiological outcome assessment at the TOC visit.

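### CE and ME membership hinges on a TOC rating even for Day 3 and EOT results, and the plan does not say whether failures and LOS deaths before TOC count as rated

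*SAP*

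**What the plan says.** Each document defines one CE and one ME population. Under SAP 4.2.2 an infant is in CE if it "received at least 48 hours of study drug and had a completed overall clinical outcome assessment at the TOC visit". Protocol 8.2.2 has the same TOC condition and lists it with two others: the patient "had a completed overall clinical outcome assessment at the TOC visit, no major protocol deviations, and no concomitant systemic non-study antibiotic therapy". SAP 4.2.2 carries those two as well. Under SAP 4.2.4, ME consists of CE infants with "a causative pathogen identified at baseline and a microbiological outcome assessment at the TOC visit". Protocol 5.2.4 places TOC 7 to 14 days after dosing ends.

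SAP 3.2.2 applies the same sets to earlier visits:

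- "Clinical cure rate at the EOT and TOC visits", in ITT and CE
- "Improved signs and symptoms of LOS at the Day 3, EOT, and TOC visits (ITT and CE populations")
- microbiological eradication or presumed eradication at EOT and TOC, in mITT and ME. ME has no Day 3 endpoint.

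Protocol 5.6.1 obliges the investigator to rate clinical outcome at both EOT and TOC. One ground for clinical failure is "Death attributable to LOS". Another is stopping study treatment and needing non-study antibacterials, because the effect was insufficient or because of a treatment-related adverse event. A missing clinical assessment falls under the unevaluable category.

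**The concern.** A denominator for Day 3 or EOT should be fixed by what is known at that visit. Here it also depends on whether a rating was completed at a visit one to two weeks after the last dose. An infant properly rated at EOT can be taken out of the EOT result by something that happens, or fails to happen, later.

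The infants most likely to lack a TOC rating are those who died or were switched to other treatment, so the loss need not be random. The trial is open-label with about eight infants. If the rule is left unstated, each membership decision would be made with outcomes known, and a single decision is visible in the reported rate.

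**Working it through.** The plan gives no expected size or rate for CE or ME, so there is no figure of its own to reproduce. The only number is the planned sample, 2 term + 6 pre-term = 8 (SAP 4.1). The check has two parts.

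**1. Tracing membership through the text**

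- *Infant rated at Day 3 and EOT, no TOC rating.* The TOC condition fails, so the infant is not in CE, and not in ME, which is nested in CE. Its Day 3 signs, EOT clinical outcome and EOT microbiological outcome leave the CE and ME tables. This needs no disputed reading.
- *Infant who dies of LOS after at least 48 h of drug and before the TOC window.* Two routes are open.
  - Kept: protocol 5.6.1 makes the death a clinical failure and requires a TOC rating. Protocol 5.6.3 then gives presumed persistence when a clinical failure has no follow-up culture.
  - Lost: no TOC visit took place and no rating is entered. SAP 4.3.4 uses observed values only and has no rule carrying a failure or death to TOC. Its one rule on survival concerns Day 28 mortality. The non-responder rule in protocol 8.4.5 classifies an unknown response but does not confer CE membership.
- *Surviving infant rated a failure at EOT.* For patients who stop treatment early, protocol 4.4 asks for every effort to complete EOT and LFU and does not name TOC, so the TOC rating may be missing.
- *Infant given non-study antibacterials because study treatment failed.* CE bars concomitant systemic non-study antibiotics, and SAP 7.1 counts any medication started after the first dose as concomitant. Read literally, this infant is out of CE even with a TOC rating.
- *Infant with less than 48 h of drug.* Out of CE by the exposure rule, whatever the TOC condition says.

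**2. Size, as an illustration**

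Assume N = 8 infants who otherwise meet CE. Let d be LOS deaths after 48 h and before TOC, and s be surviving failures with a TOC rating; everyone else is cured at TOC.

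Rate with deaths kept = (8 − d − s)/8. Rate with deaths dropped = (8 − d − s)/(8 − d).

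| d | s | Kept | Dropped | Difference |
|---|---|---|---|---|
| 1 | 0 | 7/8 = 87.5% | 7/7 = 100% | 12.5 points |
| 1 | 1 | 6/8 = 75.0% | 6/7 = 85.7% | 10.7 points |
| 2 | 0 | 6/8 = 75.0% | 6/6 = 100% | 25.0 points |
| 2 | 1 | 5/8 = 62.5% | 5/6 = 83.3% | 20.8 points |

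At EOT and Day 3 the direction depends on how the removed infant was rated there. Suppose seven of eight are cured at EOT and one has failed. Removing the failure changes 7/8 (87.5%) to 7/7 (100%). Removing one of the cured infants changes it to 6/7 (85.7%), a fall of 1.8 points.

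The documents give no rate for LOS deaths between 48 h and TOC. The 10.3% to 28.6% mortality range in protocol 1.1.1 is for neonatal sepsis in general, so it is not used here as a forecast.

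**The case against.** A reader might infer that every infant who dies of LOS before TOC drops out of all CE and ME rates. The documents do not support that. An infant who has died cannot attend a visit, so listing LOS death as a failure to be rated at TOC makes sense only if the rating can be completed after death. On that reading the infant stays in CE as a failure and in ME as presumed persistence. This is a fair reading and may be the intended one. Neither document states it, however, and the absence of any carry-forward rule leaves the other route open.

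A second objection is that an EOT failure may leave CE through the antibiotic clause anyway, so repairing the TOC condition alone would not restore that infant. That is correct, and the fix must cover both.

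Third, the consequences are limited. ITT and mITT have no TOC condition, Day 28 mortality is analysed in ITT, and all data are listed. SAP 4 plans no hypothesis test, and safety is the primary endpoint. This stands and limits the weight of the point.

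Fourth, visit-specific sets may seem heavy for about eight infants. The cost is small, though, and such a small sample is also why one infant shows in the rate.

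**Conclusion.** The point holds in a limited form. It is certain from the text that CE results at Day 3 and EOT, and ME results at EOT, exclude infants who lack a TOC rating. It is unresolved whether an EOT failure or an LOS death before the TOC window counts as a completed TOC assessment; if it does not, that infant leaves CE and ME at all visits where they are used. The antibiotic clause is a separate route by which treatment failures can leave CE. SAP 12 revisits the CE definition but clarifies only the 48-hour requirement.

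One dropped LOS death raises TOC cure by 12.5 points if all others are cured, or by 10.7 points with one surviving failure. Both figures assume that all eight infants are otherwise CE-eligible. They are not forecasts, and a uniform upward bias should not be inferred, because at Day 3 and EOT the shift can go either way. ITT, mITT and Day 28 mortality results do not change. The definitions should be corrected before database lock, but no main conclusion of the trial rests on them.

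**What to change.** Amend SAP 4.2.2 and 4.2.4, and protocol 8.2.2 and 8.2.4 to match:

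1. Define evaluability by visit. CE-EOT requires an EOT clinical assessment and serves Day 3 and EOT. ME-EOT requires an EOT microbiological assessment and serves EOT only. CE-TOC and ME-TOC require the TOC assessments and serve TOC.
2. State that a clinical failure at EOT, or an LOS-attributable death after at least 48 h of study drug and up to TOC, is carried forward as clinical failure at TOC and satisfies the TOC-assessment requirement. For ME the TOC outcome is presumed persistence if there is no follow-up culture.
3. State that non-study antibacterials started because of clinical failure do not exclude a patient from CE.

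Day 3 would still depend on an EOT rating. That is a much shorter look ahead, since EOT falls within 24 hours of the last dose.

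The cost is some SAP and protocol wording and extra population flags. The tables would carry two CE and two ME denominators, and the CE and ME rates may be slightly less favourable.

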### 5.3.2 Prohibited concomitant medications

- Systemic antibacterial therapy other than ampicillin and aminoglycosides

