#### 5.2 Protocol deviations

A protocol deviation is any change, divergence, or departure from the study design or procedures defined in the protocol. Protocol deviations will be documented by the clinical monitor throughout the course of monitoring visits. The protocol deviations will be categorized as important and non-important deviations, with important deviations further classified as major or minor (see the definition of the CE population in Section 4.2.2).

All protocol deviations will be listed, with patients with major protocol deviations leading to exclusion from CE population identified prior to database lock.

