## 7 TREATMENTS AND MEDICATIONS

### 7.1 Prior and concomitant medications

All medications, other than the study drug, used during the study (from 7 days prior to the first dose of study drug, or from 3 days prior to the first dose of study drug for medications taken by the lactating mother), must be documented on the appropriate section of the eCRF.

Prior medications are defined as medications with a stop date prior to the first dose of study drug. Concomitant medications are defined as medications that are either ongoing at the time of the first dose of study drug, or start after the first dose of study drug.

The number and percentage of patients who receive prior and/or concomitant medication will be summarized separately by ATC level 2, ATC level 4, and PT.

At each level of summarization, a patient is counted once if he/she reports one or more medications at that level. All prior medications and concomitant medications will be summarized for the ITT population.

The imputation algorithm for partial concomitant medication dates is provided in [Appendix 1](#).

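### The CE definition has no exemption for antibiotics given because study treatment failed, so rescued failures can drop out and the CE cure rate at TOC can be overstated

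*SAP*

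**What the plan says.** Besides a 48-hour minimum on study drug, SAP 4.2.2 sets this condition for CE membership: "had a completed overall clinical outcome assessment at the TOC visit, no major protocol deviations, and no concomitant systemic non-study antibiotic therapy". Protocol 8.2.2 and the synopsis carry the same condition: "no major protocol deviations, and no concomitant systemic non-study antibiotic therapy". None of the three distinguishes antibiotics by the reason they were given.

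Protocol 5.6.1 gives two routes to clinical failure. The non-fatal one is "Discontinuation of study treatment and requirement for non-study antibacterial therapy because of" either insufficient effect or an "AE related to the study treatment". The other is death attributable to LOS. The unevaluable category in the same section does look at the reason: "Concomitant treatment with a systemic antibacterial administered for a reason other than LOS, which is active against the isolated LOS pathogen".

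The SAP defines concomitant medication once, in 7.1, as medication that is either "ongoing at the time of the first dose of study drug, or start after the first dose of study drug". The definition has no end date. Protocol Table 3 likewise records concomitant medication through LFU.

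CE cure rate at EOT and TOC is a secondary endpoint (SAP 3.2.2), and ME is a subset of CE (SAP 4.2.4). SAP 12 reports no changes from the protocol and clarifies only the 48-hour condition of CE.

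**The concern.** For a survivor, the event that establishes failure is the need for a non-study antibacterial, and that antibacterial meets the CE exclusion if concomitant has its SAP 7.1 meaning. CE would then lose rescued failures because they failed, while cured patients who need nothing further stay in.

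A second feature adds to the loss. CE needs a TOC assessment, but for patients who discontinue treatment protocol 4.4 asks sites to make every effort to complete EOT and LFU and does not name TOC. Non-fatal failures are discontinuers by definition.

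At stake is whether the CE cure rate can be interpreted. Two programmers could apply the same sentence to the same eight patients and report quite different rates. Because the study is open-label, whoever settles the wording late may already know the outcomes.

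**Working it through.** The plan states no expected cure rate, failure rate or CE size, so there is no figure of its own to reproduce. The effect follows by counting.

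**Inputs.** N = 8 (two term, six pre-term; SAP 4.1). Protocol 4.6 closes each group once its minimum is reached, so eight is the natural base case. Assumed: all eight are otherwise CE-eligible with at least 48 hours of study drug, none is unevaluable, and rescue uses an agent other than ampicillin or an aminoglycoside. Numbers of failures and rescues are assumed throughout.

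**TOC.** With c cures at TOC and r rescued failures, the cure rate is c/N if they are kept and c/(N − r) as written. With at least one cure, the second is larger whenever r > 0.

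| Failures | Rescued | Kept | As written |
|---|---|---|---|
| 1 | 1 | 7/8 = 87.5% | 7/7 = 100% |
| 2 | 2 | 6/8 = 75% | 6/6 = 100% |
| 3 | 3 | 5/8 = 62.5% | 5/5 = 100% |
| 2 | 1 | 6/8 = 75% | 6/7 = 85.7% |
| 3 | 1 | 5/8 = 62.5% | 5/7 = 71.4% |
| 3 | 2 | 5/8 = 62.5% | 5/6 = 83.3% |

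If no failure is rescued there is no gap. An unrescued failure in the table is, for example, an LOS death with a TOC outcome on record.

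For failure probability p and rescued share s, the expected-count rate as written is (1 − p)/(1 − s·p). For p = 10%, 20%, 30% (cure 90%, 80%, 70%):
- s = 50%: 94.7%, 88.9%, 82.4%
- s = 75%: 97.3%, 94.1%, 90.3%
- s = 100%: 100% throughout

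The chance of at least one failure among eight, 1 − (1 − p)^8, is 57.0%, 83.2% and 94.2% for the same p.

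**EOT.** CE is one population used at both visits. Take a patient rated cured at EOT who starts a non-study antibiotic before TOC, plus one other patient who failed and stays in CE. EOT cure is 7/8 = 87.5% if the first patient is kept and 6/7 = 85.7% if removed, so it falls. If the other failure was also rescued and removed, it becomes 6/6 = 100%. The direction is not fixed.

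**After TOC.** SAP 7.1 sets no end date, so an antibiotic for relapse between TOC and LFU would remove a patient already rated cured at TOC. With seven cures, one of them so treated, and one failure retained, TOC cure goes from 7/8 = 87.5% to 6/7 = 85.7%.

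**ME.** Assume four patients with a baseline pathogen (range 3 to 6) and one rescued failure removed.
- Removed patient had presumed persistence, no other persistence: 3/4 = 75% kept (66.7% to 83.3%), 3/3 = 100% as written.
- Removed patient had documented eradication, one retained patient has persistence: 3/4 = 75% kept (66.7% to 83.3%), 2/3 = 66.7% as written (50% to 80%).
- Removed patient had documented eradication, no other persistence: 100% either way.

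The second case can arise because protocol 5.6.3 bases eradication on follow-up cultures and 5.4 asks for repeat cultures until sterile.

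**The case against.** The best reply is that SAP 4.2.2 does not refer to 7.1. Section 7.1 sorts drugs into prior and concomitant tables, and the Table 3 footnote is a recording rule; neither is written as a CE rule. Protocol 5.6.1 speaks of concomitant treatment for a confounding drug but of discontinuation and a requirement for other therapy for rescue. SAP 8.1 also tabulates reasons for failure in CE. Under the broad reading that table could hold little beyond LOS deaths and failures rescued with permitted agents. This stands as a good argument that the sponsor may intend concomitant to mean alongside ceftobiprole. It does not settle the matter: that meaning is not stated for CE, and the only definition in the SAP says otherwise.

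Three stronger readings are tempting and are not supported:
- A reader might infer that the wording can only favour the drug. The EOT and post-TOC examples show otherwise.
- A reader might infer that the ME eradication rate is inflated too. It can rise, fall or stay the same.
- A reader might infer that rescue is a major deviation, because protocol 5.3.2 prohibits "Systemic antibacterial therapy other than ampicillin and aminoglycosides" without a time limit and SAP 5.2 lists deviations "with patients with major protocol deviations leading to exclusion from CE population identified prior to database lock". Nothing classes rescue as major. Protocol 1.3.3 anticipates management with other therapies, 3.3.1 anticipates a switch to standard of care, and 5.3.2 turns on the same undefined word.

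It is also fair that nothing is tested, the primary endpoint is safety, and all data are listed by patient, so with about eight patients a removed failure would be visible.

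**Conclusion.** The concern holds as a gap in the CE definition. Following the SAP's own terms, rescued failures leave CE, and the CE cure rate at TOC is then overstated: by 12.5, 25 or 37.5 points for one, two or three failures among eight if all are rescued and otherwise eligible, less if only some are, and not at all if none is. These sizes rest on assumed failure and rescue counts and on the SAP 7.1 meaning of concomitant; under the narrower meaning, patients rescued after stopping ceftobiprole stay in, provided they have a TOC assessment. No fixed direction can be claimed for EOT or ME.

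The consequence is confined to descriptive secondary results. No decision rule uses CE or ME, and the ITT cure rate keeps these failures. It is still worth correcting, because one sentence decides whether a named endpoint is interpretable.

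**What to change.** Amend SAP 4.2.2 before database lock:

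1. Keep the exclusion for non-study systemic antibacterials given during ceftobiprole treatment, including any added for LOS, or given for another reason up to TOC.
2. Add that antibiotics started because the patient met a protocol 5.6.1 clinical-failure criterion do not exclude the patient from CE and are not by themselves a major deviation.
3. State that the exclusion period ends at the TOC assessment.
4. State that patients with at least 48 hours of study drug who are failures at EOT, or who die from LOS before TOC, stay in CE as failures at TOC.

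Borrowing the unevaluable rule's limit to antibacterials given for reasons other than LOS would not be enough. A patient who had a non-study antibiotic added for LOS while still on ceftobiprole has not discontinued, could be rated cured, and would then enter CE; item 1 keeps that patient out.

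Record the change in SAP 12 as made without reference to individual outcomes, and say there that it departs from protocol 8.2.2 and the synopsis until both are aligned at the next amendment. Protocol section 8 calls for an amendment only when a principal feature is altered. The cost is a few sentences and no new data; the downside is a possibly less favourable CE cure rate. The change concerns analysis membership only and leaves patient management untouched.

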## 3 STUDY DESIGN

This is a multicenter, open-label, single-arm, multiple-dose study of IV ceftobiprole in term and pre-term neonates and infants up to 3 months of age with LOS. At least eight patients, at least two term (gestational age  $\geq 37$  weeks) and at least six pre-term (gestational age  $\geq 24$  to 36 weeks), with post-natal age ranging from  $\geq 3$  days to  $\leq 3$  months will be enrolled at approximately ten sites in Europe and USA, with additional sites and locations possible.

Study therapy consists of IV ceftobiprole medocaril for 3–10 days, which may be extended to 14 days if considered clinically necessary by the Investigator. Ceftobiprole may be combined with ampicillin and/or an aminoglycoside based on the Investigator's judgement, local standard of care, and/or isolated or presumed pathogens. If added, the treatment duration of ampicillin and/or an aminoglycoside is at the discretion of the Investigator.

Each patient is expected to complete the study in approximately 5–7 weeks, including screening, an estimated treatment duration of 3–10 days with possible extension up to 14 days, end-of-treatment (EOT) visit, TOC visit 7–14 days after last ceftobiprole dose, and a last follow-up (LFU) visit 28–35 days after last ceftobiprole dose.

[figure not shown]
Safety assessments will be done throughout the study. Specimens for microbiological assessment will be obtained as clinically indicated in accordance with local standard of care. Blood samples for PK analysis will be collected on Day 3. Efficacy outcomes will be assessed at the EOT, TOC, and LFU visits.

The DSMB will review data on a regular basis to assess the safety of all patients enrolled in this study (see Section 3.4).

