### 5.2.5 Last follow-up visit

The following assessments and procedures will be performed at the LFU visit (28–35 days after the last dose of study drug; see Table 3). This visit can be done by telephone contact unless an examination is needed to evaluate relapse or abnormalities recorded during the TOC visit.

- Review and recording of changes in concomitant medications and concomitant procedures
- Adverse events must be monitored and recorded as outlined Section 7.4.
- Survival status
- Relapse assessment: Deterioration of the clinical condition compared to the TOC visit, microbiological recurrence, or the requirement for additional antimicrobial therapy for LOS

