#### **5.6.4 Relapse at LFU**

At the LFU visit, the Investigator must assess relapse as follows:

- Deterioration of the patient's clinical condition compared to the TOC visit, microbiological recurrence, or the requirement for additional antimicrobial therapy for LOS

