### 8.3 Microbiological response

Microbiological outcome is to be assessed at the EOT and TOC visits by the Investigator as ‘Eradication’, ‘Presumed eradication’, ‘Persistence’, ‘Presumed persistence’, ‘Unevaluable’, or ‘Relapse’ (see protocol Section 5.6.3 for details). If applicable, the relapse status of the patient is to be assessed at the LFU visit, by the Investigator.

Patients will be considered to have experienced microbiological eradication if they are classified as ‘Eradication’ or ‘Presumed eradication’. Microbiological eradication at EOT and TOC, and relapse status at the LFU visit, will be summarized in a table for the mITT and ME populations.

All microbiological data will be listed.

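### The CE antibiotic exclusion has no end point, so a non-study antibiotic started after TOC removes an infant from CE and ME and biases ME relapse towards zero

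*SAP*

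**What the plan says.** - **CE membership.** SAP 4.2.2 requires at least 48 hours of study drug, a completed clinical outcome assessment at TOC, no major deviation and "no concomitant systemic non-study antibiotic therapy". Protocol 8.2.2 has the same condition: "no major protocol deviations, and no concomitant systemic non-study antibiotic therapy". Neither gives a start or an end for the antibiotic condition.
- **Meaning of concomitant.** The SAP's only definition of a concomitant medication is in section 7.1: "either ongoing at the time of the first dose of study drug, or start after the first dose of study drug". There is no upper limit. The companion definition reads: "Prior medications are defined as medications with a stop date prior to the first dose of study drug".
- **Recording period.** The LFU procedures in protocol 5.2.5 include "Review and recording of changes in concomitant medications and concomitant procedures", so drugs started after TOC are in the database.
- **Nesting.** SAP 4.2.4 and protocol 8.2.4 make ME a subset of CE.
- **Relapse.** Protocol 5.6.4 defines relapse at LFU as clinical deterioration since TOC, "microbiological recurrence, or the requirement for additional antimicrobial therapy for LOS". SAP 8.3 states that "relapse status at the LFU visit, will be summarized in a table for the mITT and ME populations".
- **Nothing elsewhere closes the window.** Protocol 5.3.2 (prohibited medications) and SAP 5.2 (deviations) give no period. SAP 12 clarifies only the 48-hour rule for CE.

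**The concern.** CE is used for clinical outcome at EOT and TOC and for signs and symptoms up to TOC. ME is used for microbiological outcome at the same two visits. An antibiotic started after TOC cannot change any of these results, yet it decides whether the infant is counted. That is selection on an event later than the outcome.

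Relapse is affected more directly. The need for further antimicrobial therapy is one of the criteria that define relapse, and the same therapy, if it is a systemic non-study antibacterial, removes the infant from one of the two populations in which relapse is tabulated. The protocol describes no second course of ceftobiprole, so treatment of a relapse with another agent is foreseeable. The ME relapse figure would then look better than the data because of how the population is built.

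**Working it through.** The plan gives no figure on this point to reproduce. The check is a trace through the definitions, with small counts for scale.

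**1. Length of the open period after TOC.** Protocol section 3 places the "TOC visit 7–14 days after last ceftobiprole dose" and LFU 28 to 35 days after it.
- Shortest gap: 28 − 14 = 14 days.
- Longest gap: 35 − 7 = 28 days.

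**2. Trace for one infant.** The infant is cured at TOC with the baseline pathogen eradicated, relapses before LFU and receives a systemic antibacterial other than ceftobiprole, ampicillin or an aminoglycoside.
- SAP 7.1: the drug started after the first dose, so it is concomitant.
- SAP 4.2.2: the infant leaves CE.
- SAP 4.2.4: the infant therefore leaves ME.
- SAP 8.3: the relapse is counted in mITT and not in ME.

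**3. Effect on the relapse table.** Assume exactly one such relapse, and that all n mITT infants otherwise qualify for ME. Under SAP section 4 the denominator is the whole population of interest. The values of n are assumptions, since the plan does not predict the size of mITT.

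| n in mITT | mITT, 1/n | ME as written, 0/(n − 1) | ME with exclusion ending at TOC, 1/n |
|---|---|---|---|
| 2 | 50.0% | 0/1 | 50.0% |
| 4 | 25.0% | 0/3 | 25.0% |
| 6 | 16.7% | 0/5 | 16.7% |
| 8 | 12.5% | 0/7 | 12.5% |

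For this kind of relapse the ME numerator is zero at every n.

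**4. Effect on CE cure.** Suppose 7 of 8 infants are cured in ITT (87.5%) and all eight otherwise qualify for CE. If 1, 2 or 3 cured infants are removed for a later antibiotic, CE shows 6/7 (85.7%), 5/6 (83.3%) or 4/5 (80.0%). The TOC results themselves are unchanged.

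**5. How often this might happen.** Let p be the chance that an infant starts a systemic non-study antibiotic after TOC. The documents give no value, so p is an assumption. With eight independent infants, the chance that at least one is removed is 1 − (1 − p)^8:
- p = 5%: 33.7%
- p = 10%: 57.0%
- p = 20%: 83.2%
- p = 30%: 94.2%

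**The case against.** **SAP 7.1 may not govern CE.** It sits in the medication-summary section, and SAP 4.2.2 does not cite it. Protocol 5.6.1 also uses the idea of concomitant systemic antibacterial treatment, as a reason to rate an outcome unevaluable at EOT or TOC, where it cannot reach past the visit being rated. The ambiguity is real, but that passage governs the rating of a visit and not membership of CE. The only definition a programmer would find in the SAP is the open-ended one.

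**A reader might infer that a treated relapse can never appear in the ME table.** The documents do not support that. Ampicillin and aminoglycosides are permitted, and the term non-study is not defined, so a relapse treated only with them may stay in ME. The relapse definition also speaks of antimicrobial therapy, which is wider than antibacterial therapy, and it can be met without any treatment.

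**A reader might also infer that an antibiotic stopped on the day of the first dose always removes the infant.** The text does not settle this. A drug stopped earlier that day does not have a stop date before the first-dose date, so it is not clearly prior. Nor was it ongoing at the first dose, so it is not clearly concomitant. It would exclude the infant only if dates alone were compared and everything not prior were treated as concomitant. The case is foreseeable, because exclusion criterion 12 allows up to 72 hours of earlier systemic antibacterials, but it calls for a clarification only.

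**The consequence is small.** This stands. The primary endpoint is safety, nothing is tested, and relapse is not a listed secondary endpoint. ITT and mITT results are unaffected, and with about eight infants the listings would show who is missing from ME.

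**Conclusion.** The concern holds in a limited form. The CE antibiotic exclusion has no end point. Under the SAP's own definition, a systemic non-study antibacterial started after TOC removes an infant from CE and ME once the outcomes those populations support are fixed. Relapses treated that way are lost from ME, so ME relapse is biased towards zero.

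The direction follows from the definitions. The size does not: 25% against 0% assumes one such relapse, four mITT infants and all four otherwise in ME. The bias affects supportive, descriptive populations only, and every such relapse in an mITT infant remains in the mITT table and the listings. It is still worth correcting before database lock, because the fix is short and the ME relapse figure cannot be taken at face value without it.

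This point concerns only where the window ends. How non-study antibiotics given for failure before TOC should affect CE is a separate question.

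**What to change.** **Main change.** In SAP 4.2.2, limit the exclusion to systemic non-study antibacterials given from the first dose of ceftobiprole up to the TOC assessment. State that antibiotics started after TOC do not affect CE or ME membership.

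**Secondary clarifications, in the same place.**
- State that a prior antibacterial whose last dose was on the date of the first ceftobiprole dose is not counted as concomitant for this purpose.
- Define non-study, for this analysis, as systemic antibacterials other than ceftobiprole, ampicillin and aminoglycosides.

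**Protocol.** Align section 8.2.2 at the next amendment. Protocol section 8 requires an amendment only when a principal feature changes, so the SAP clarification need not wait for the ethics review that section 9.4 attaches to amendments.

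**Cost.** A few sentences before database lock and a date condition in the population derivation. No new data are needed and no infant's care changes. The one downside is that an infant with a few hours of antibiotic overlap on Day 1 stays in CE.
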